3.3.4.1 Hepatobiliary Laboratory Abnormalities

The number and percentage of patients falling in each of the following categories based on all post-baseline assessments of the OLE study, including scheduled and unscheduled assessment on-study

period which spans the time drug is administered until the day of the patient's last contact date within the study, will be provided:

- ALT ≥ 3x Upper limit of normal (ULN) and total bilirubin ≥ 2xULN (with both events for any postbaseline results)
- Confirmed ALT ≥ 3x Upper limit of normal (ULN) and confirmed total bilirubin ≥ 2xULN (with both events for any post-baseline results)
- ALT ≥ 3xULN and international normalized ratio > 1.5 (with both events for post-baseline results)
- ALT ≥ 3xULN and total bilirubin ≥ 2xULN and ALP < 2xULN (with all three events for any postbaseline results)
- Hepatocellular injury
- Hepatocellular injury and total bilirubin ≥ 2xULN (with both events for any post-baseline results)
- ALT ≥ 3xULN
- ALT ≥ 5xULN
- ALT ≥ 8xULN
- ALT ≥ 10xULN
- ALT ≥ 20xULN
- Confirmed ALT ≥ 3xULN
- Confirmed ALT ≥ 5xULN
- Confirmed ALT ≥ 8xULN
- Confirmed ALT ≥ 10xULN
- Confirmed ALT ≥ 20xULN
- ALT ≥ 3xULN < 5xULN
- ALT ≥ 5xULN < 10xULN
- ALT ≥ 10xULN < 20xULN
- Total bilirubin ≥ 2xULN
- ALP ≥ 2xULN and (ISIS 420915 baseline ALP < 2xULN or ISIS 420915 baseline ALP missing)
- ALT \geq 3x ULN and ALT \geq 2 x ISIS 420915 baseline
- Confirmed ALT ≥ 3x ULN and confirmed ALT ≥ 2 x ISIS 420915 baseline

For patients that had ALT elevation ≥ 3 xULN, the time from CS3 Study Day 1 to first ALT elevation ≥ 3 xULN will be summarized using the following descriptive statistics: mean, standard deviation, median, P25, P75, and minimum and maximum.

Shift tables from baseline for ALT, AST, and total bilirubin based on peak (maximum) and confirmed peak category will also be provided. Categories for the ALT and AST shift tables will be $< 3 \times ULN$, $\ge 3 \times ULN$, $\ge 5 \times ULN$, and $\ge 8 \times ULN$. Categories for the total bilirubin shift table will be $< 2 \times ULN$ and $\ge 2 \times ULN$.

A hepatocellular injury event is defined as $(ALT/ALT\ ULN)/(ALP/ALP\ ULN) \ge 5$ and $ALT \ge 3xULN$, with the ALT and ALP assessments done on the same day.

The categories listed above will also be analyzed using AST instead of ALT. For these analyses the definition of hepatocellular injury will not be changed to depend on AST.

3.3.4.2 *Platelets*

The number and percentage of patients falling in each of the following categories (using available central and local laboratory assessments combined) based on post-baseline assessments, including scheduled and unscheduled assessment on-study period which spans the time drug is administered until the day of the patient's last contact date within the study, will be provided:

- Platelet count decrease Grade 1a [≥ 100 10^9/L to < 140 x 10^9/L]
- Platelet count decrease Grade 1b [≥ 75 10^9/L to < 100 x 10^9/L]
- Platelet count decrease Grade 2 [[≥ 50 10^9/L to < 75 x 10^9/L]
- Platelet count decrease Grade 3 [≥ 25 10^9/L to < 50 x 10^9/L]
- Platelet count decrease Grade 4 [< 25 x 10^9/L]
- Confirmed Platelet count decrease Grade 1a [≥ 100 10^9/L to < 140 x 10^9/L]
- Confirmed Platelet count decrease Grade 1b [≥ 75 10^9/L to < 100 x 10^9/L]
- Confirmed Platelet count decrease Grade 2 [[≥ 50 10^9/L to < 75 x 10^9/L]
- Confirmed Platelet count decrease Grade 3 [≥ 25 10^9/L to < 50 x 10^9/L]
- Confirmed Platelet count decrease Grade 4 [< 25 x 10^9/L]
- Maximum toxicity grade (Grade 1a, Grade 1b, Grade 2, Grade 3, Grade 4)
- Confirmed maximum toxicity grade (Grade 1a, Grade 1b, Grade 2, Grade 3, Grade 4)
- Value < 140 x 10^9/L
- Confirmed ≥ 30% decrease from the ISIS 420915 baseline
- Confirmed ≥ 50% decrease from the ISIS 420915 baseline
- Confirmed value < 140 x 10^9/L
- Confirmed value < 100 x 10^9/L
- Confirmed value < 75 x 10^9/L
- Confirmed value < 50 x 10^9/L
- Confirmed value < 25 x 10^9/L

Note that a platelet value of 140×10^9 /L is the lower limit of normal for the central laboratory and will be used as the LLN for all platelet assessments. Furthermore, the platelet counts that define platelet count decrease grades are based on interactions with a regulatory authority, and align with the definitions from the National Cancer Institute Common Terminology Criteria for Adverse Events version 4.03 (except that the CTCAE does not subdivide Grade 1 into Grade 1a and 1b).

Shift tables from baseline will be provided using the nadir value and the confirmed nadir category. Categories for the shift table will be $\geq 140 \times 10^{9}/L$, $\geq 100 \times 10^{9}/L$ to $< 140 \times 10^{9}/L$, $\geq 75 \times 10^{9}/L$ to $< 100 \times 10^{9}/L$, $\geq 50 \times 10^{9}/L$ to $< 75 \times 10^{9}/L$, $\geq 25 \times 10^{9}/L$ to $< 50 \times 10^{9}/L$, and $< 25 \times 10^{9}/L$.

Time from **CS3 Study Day 1** to the onset of each of these events collected in the OLE study will be summarized for the patients in SS that met the criterion. Summaries including the following descriptive statistics: mean, standard deviation, median, P25, P75, and minimum and maximum.

Kaplan-Meier plots for time to first event will also be provided for value < 140×10^9 /L, value < 100×10^9 /L and value < 75×10^9 /L.

The post-baseline nadir (absolute value, change from the **ISIS 420915 baseline**, and percent change from the **ISIS 420915 baseline**) of platelet count will be summarized by treatment group of the parent study.

Duration of platelet counts below the $140 \times 10^9/L$ will be summarized, based on the duration (in weeks) each patient was below the $140 \times 10^9/L$.

The above analyses will be repeated for the subgroups defined by CM-ECHO Set.

Scatter plots for nadir platlets versus the **ISIS 420915 baseline** of BMI, mBMI, and weight will be provided.

A listing of patients with dose pause due to Platelet < 75 x10^9/L will also be provided.

3.3.4.3 Renal Parameters

The number and percentage of patients falling in each of the following categories (using available central laboratory assessments) based on post-baseline assessments, including scheduled and unscheduled assessment on-study period which spans the time drug is administered until the day of the patient's last contact date within the study, will be provided:

- Creatinine clearance by CKD-EPI < 90 mL/min/1.73m²
- Creatinine clearance by CKD-EPI < 60 mL/min/1.73m²
- Creatinine clearance by CKD-EPI < 30 mL/min/1.73m²
- Creatinine clearance by CKD-EPI < 15 mL/min/1.73m²
- Creatinine clearance by CKD-EPI ≥ 25% decrease from the ISIS 420915 baseline
- Creatinine clearance by CKD-EPI ≥ 50% decrease from the ISIS 420915 baseline
- Urine Alb/C ratio > 5 x ULN
- Urine P/C ratio > 5 x ULN
- Serum creatinine increase > 44.2 umol/l (0.5 mg/dL) from the ISIS 420915 baseline
- Confirmed creatinine clearance by CKD-EPI < 90 mL/min/1.73m²
- Confirmed creatinine clearance by CKD-EPI < 60 mL/min/1.73m²
- Confirmed creatinine clearance by CKD-EPI < 30 mL/min/1.73m²
- Confirmed creatinine clearance by CKD-EPI < 15 mL/min/1.73m²
- Confirmed creatinine clearance by CKD-EPI ≥ 25% decrease from the ISIS 420915 baseline
- Confirmed creatinine clearance by CKD-EPI ≥ 50% decrease from the ISIS 420915 baseline
- Confirmed urine Alb/C ratio > 5 x ULN
- Confirmed urine P/C ratio > 5 x ULN
- Confirmed serum creatinine increase > 44.2 umol/I (0.5 mg/dL) from the ISIS 420915 baseline

Shift tables from baseline for creatinine clearance by CKD-EPI will be provided using the nadir value and the confirmed nadir category. Categories for the shift table will be $\geq 90 \text{ mL/min/}1.73\text{m}^2$, $\geq 60 \text{ mL/min/}1.73\text{m}^2$

mL/min/1.73m² to < 90 mL/min/1.73m² , \geq 30 mL/min/1.73m² to < 60 mL/min/1.73m² , \geq 15 mL/min/1.73m² to < 30 mL/min/1.73m², and <15 mL/min/1.73m².

Shift tables from baseline for hemoglobin will be provided using the nadir value. Categories for the shift table will be Grade 0 (≥LLN, Absent), Grade 1 (< LLN - 100.0 g/L, Mild), Grade 2 (< 100.0 - 80.0 g/L, Moderate) and Grade 3 (< 80.0 g/L, Severe).

The above analyses will be repeated for the subgroups defined by CM-ECHO Set.

3.3.4.4 Longitudinal Safety Analysis of Laboratory Measurements

Laboratory measurements summaries including data from the combined study periods of the parent and OLE studies will be provided for subjects in the LSS analysis population. These summaries will include lab results specified in this section which occurred on or after the first dose of ISIS420915 in the parent study and before the day of the patient's last contact date For subjects who enrolled in the OLE study, the last contact date would be the one obtained from the OLE study. For subjects who are not enrolled in the OLE study, the last contact date would be the one obtained from the parent study:

- Hepatobiliary laboratory abnormalities (defined in section 3.3.4.1);
- Platelets (defined in section 3.3.4.2);

Note: For longitudinal safety analysis, Time to events will be started from **Day 1 of ISIS 420915** instead of **Study Day 1**.

• Renal parameters (defined in section 3.3.4.3)

Summaries for these abnormal lab test results will be provided for patients on active treatment in the parent study in LSS.

3.3.5 Electrocardiograms

Absolute value, change and percent change from the **ISIS 420915 baseline** in ventricular rate and ECG intervals (PR, QRS, QT, QT interval corrected for heart rate interval calculated using Fridericia's formula [QTcF], QT interval corrected for heart rate int erval calculated using Bazett's formula [QTcB]) will be presented by treatment group of the parent study and visit. Shift tables from the **ISIS 420915 baseline** to the worst (highest) post-baseline value by treatment group of the parent study will be used to assess the change in the QTcF interval. The categories for the shift table will be: **4**50 msec, >450 msec to ≤ 480 msec, >480 msec to ≤ 500 msec, and > 500 msec. The number and percent of patients experiencing an increase from baseline in QTcF interval of greater than 30 msec or 60 msec at any time post-baseline will be summarized by treatment group of the parent study. This analysis will be presented overall and also by the subgroup whose QTcF was normal at the **ISIS 420915 baseline**. Normal QTcF will be defined as **4**50 msec for males or **4**70 msec for females. The number and percent of patients with overall qualitative ECG abnormalities will also be summarized. These analyses will be repeated for patients in the CM-ECHO Set. No statistical comparisons between treatments will be performed for these summaries.

Ventricular rate and ECG intervals (PR, QRS, QT, QTcF, QTcB), as well as treatment-emergent abnormalities, will be listed. The number and percent of patients that stopped treatment because they met a protocol-defined stopping rule for QT interval corrected for heart rate prolongation will be tabulated by treatment group of the parent study. This tabulation will be repeated for patients in the CM-ECHO Set.

The ECG over-read data are used to support medical monitoring and will not be used for the ECG summary and analysis. A by-subject listing of ECG over-read data will be provided.

3.3.6 Electroretinograms (ERG) and Ophthalmology Exam

Change from the **ISIS 420915 baselines** in ERG results will be summarized by treatment group of the parent study.

ERG results will be listed. Ophthalmology exam findings will be listed. The number and percent of patients reaching protocol defined stopping rules for ocular effects will be tabulated by treatment group of the parent study.

3.4 Efficacy Analyses

All analyses and summaries by visits will be performed based on analysis visits defined in the section 3.2.1.3 "Analysis Visit Windows".

3.4.1 Descriptive Statistics

For all efficacy endpoints, descriptive summary statistics for absolute values, change or percent change from baseline, if applicable, will be provided by analysis visits for FAS and PPS.

For change or percent change from the **parent study baseline**, analysis visits are defined for Week 35 and Week 65 or 66, if applicable, from the parent study and for Week 26, Week 52, Week 78, Week 104, Week 130 and Week 156 in the OLE study. Analysis visits of Year 4 Week 52 and Year 5 Week 52 will also be included for NIS, Norfolk QOL-DN, SF-36 Questionnaire and PND Score.

For change or percent change from the **OLE study baseline**, analysis visits are defined for Week 26, Week 52, Week 78, Week 104, Week 130 and Week 156 in the OLE study. Analysis visits of Year 4 Week 52 and Year 5 Week 52 will also be included for NIS, Norfolk QOL-DN, SF-36 Questionnaire and PND Score.

By patient listings for all efficacy endpoints will be provided.

For the two primary endpoints (mNIS+7 score and Norfolk QOL-DN total score), data collected outside the analysis windows in the OLE study, e.g. before Week 26, Week 26 to Week 52, Week 52 to Week 78, Week 78 to Week 104, Week 104 to Week 130, Week 130 to Week 156, and after Week 156 will not be summarized. These data will be included in the listings.

For mNIS+7 score and Norfolk QOL-DN total score, descriptive statistics by subgroup and treatment groups of the parent study will also be provided for the following subgroups:

• Stratification factor: V30M TTR mutation (Yes, No)

- Age at the parent study screening (< 65 years old, ≥ 65 years old)
- Race (White, non-White)
- Sex (Male, Female)
- Region (North America, Europe, South America / Australasia)
- Previous treatment with Vyndagel® or Diflunisal (Yes, No) prior to the parent study
- Disease stage at the parent study screening (Stage 1, Stage 2)
- CM-ECHO Set (Included, Not included)
- Through the whole OLE study, if the patient took any Vyndaqel® (Yes, No)

3.4.2 Efficacy Endpoints: mNIS+7 Score and Components, Norfolk QOL-DN Total Score and Domain Scores

The efficacy endpoints that are statistically analyzed are the following

- Change and percent change in the mNIS+7 score from either the **parent study baseline** or the **OLE study baseline** to Week 78 and Week 156
- Change in the Norfolk QOL-DN questionnaire total score from either the parent study baseline or the OLE study baseline to Week 78 and Week 156
- Change in the mNIS+7 components (NIS, heat-pain sensory, touch-pressure sensory, nerve
 conduction and heart rate to deep breathing tests) from either the parent study baseline or the
 OLE study baseline to Week 78 and Week 156
- Change in the Norfolk QOL-DN questionnaire domain scores (symptoms domain score for Stage 1 patients, and physical functioning/large fiber neuropathy domain score for Stage 2 patients) from either the parent study baseline or the OLE study baseline to Week 78 and Week 156

The maximum mNIS+7 composite score is 346.32 points. It can be broken into two components: the NIS component (maximum of 244 points) and the modified +7 component (maximum of 102.32 points). It can be further divided into the following 8 components: cranial nerves, muscle weakness, reflexes, sensory, heart rate deep breathing, nerve conduction, touch-pressure sensory, and heatpain sensory.

The normal deviates (nds) from heart rate deep breathing and nerve conduction will be used in calculation of mNIS+7.

The mNIS+7 assessment is conducted at the parent study baseline (2 times), Week 35, 66 (2 times), the OLE study Week 26, 52, 78 (2 times), 104, 130 and 156 (2 times) visit. For visits where repeated assessments are done, the average will be used for analysis. Subcomponent scores will be averaged first, and the average composite score will be computed by summing the averaged subcomponent scores.

3.4.2.1 Additional Efficacy Analysis on the Change from the Parent Study Baseline

The following additional analysis will be done for mNIS+7 score and Norfolk QOL-DN total score:

- **Degree of Progression** The degree of progression in the parent study and this OLE study will be summarized using the FAS. The degree of progression is defined as the change in the endpoint per one month. The degree of progression and corresponding 95% CI will be derived separately for each treatment group. A plot of degree of progression over time by treatment group assigned in the parent study will also be provided. The degree of progression will be derived over the 15 months treatment period of the parent study and then over 12 months treatment intervals in the OLE study. The degree of progression will be summariezed described in section 3.4.1as follows:
 - Average monthly progression over the first 15 months (i.e. from the first dose administered to Week 66 in the parent study) will be derived by dividing the estimated change from parent study baseline to Week 66 by 15.
 - Average monthly progression over the first 12 month interval in the OLE study will be estimated by dividing the estimated change from Week 66 in the parent study to Week 52 in this OLE study by 12.
 - Average monthly progression over the second 12 month interval in the OLE study will be estimated by dividing the estimated change from Weeks 52 to Week 104 in this OLE by 12.
 - Average monthly progression over the third 12 month interval in the OLE study will be estimated by dividing the estimated change from Weeks 104 to Week 156 in this OLE by 12.
- Responder Analysis for mNIS+7 score A responder analysis based on the change in mNIS+7 score will be conducted to examine whether improvement in response is consistent over a range of response thresholds using the OLE study FAS. A responders is defined as a patient whose mNIS +7 score change from the parent study baseline to the respective post-baseline visit in the OLE study, i.e. Weeks 26, 52, 78, 104, 130, 156 from the OLE study, is less than or equal to the threshold value. Threshold values to be tested will include 0, 2, 4, 6, 8, 10, 15, 20, 30 points above the baseline values. For each response threshold, the response rates at each post-baseline visit in the OLE study for both the treated group and the placebo group will be calculated and plotted against the response threshold. Evaluable patients that terminate treatment early irrespective of the reason or had missing the respective post-baseline visit in the OLE study data will be considered a non-responder. Because a patient may not be followed in the OLE long enough to contribute data at a visit, the analysis at a visit is limited to evaluable patients, defined as patients who are in the study longer than the upper bound of analysis visit window for that visit (see Table 1 of Appendix 3 Analysis Visit Windows). For example, the week 26 window extends up to day 206, and a patient would be considered evaluable at Week 26 if (data cut date – first dose date) was more than 206 days.

The efficacy analyses described in this section will be repeated using the OLE study PPS.

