3.2.2 Patient Populations Analyzed

The following analysis populations are defined for this present OLE study:

- Screened patients will be defined as patients who signed an informed consent form.
- Enrolled patients will be defined as patients who signed an informed consent form and were not screen failures.
- The FAS will include all enrolled patients who received at least 1 injection of ISIS420915 in the
 OLE study and who have at least one post-baseline efficacy assessment for the mNIS+7 score or
 Norfolk QOL-DN questionnaire total score collected after CS3 Study Day 1 in this OLE study. This
 will be the primary population for analysis of efficacy and PD outcomes.
- The Safety Set (SS) will include all enrolled patients who received at least 1 injection of ISIS
 420915 in the OLE study. This population will beused for analyses of all safety measures
 collected in this OLE study. Results will be summarized under the treatment which the patients
 received in the parent study.
- The Longitudinal Safety Set (LSS): will include all patients who received at least 1 injection of ISIS 420915 in the parent study. This population will beused for the longitudinal safety analysis for either the parent study or this OLE study. Results will besummarized under the treatment which the patients received in the parent study. Note that this population will include patients who receive ISIS 420915 in the parent study but did not enter this OLE. It does not include patients who took placebo in CS2.
- The PPS will include the subset of the Full Analysis Set that have received at least 70% of the prescribed doses of ISIS 420915 in this OLE study and that have no significant protocol deviations in the OLE study that would be expected to affect efficacy assessments. Prescribed doses of ISIS420915 mentioned above is defined as the total assigned dose in mg from the Week 1 to the last dose within this study up to week 156 (first three years), i.e. 300mg*156 doses= 46800mg. Patients in FAS of this OLE study but excluded from PPS in the parent study will be excluded from the PPS in this OLE study as well. This will be a secondary population for

efficacy and PD analyses. The detailed criteria and definitions for major protocol violations will be specified. Results will be summarized under the treatment which the patients received in the parent study.

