9.2.2.3 Itegrated Summary of Efficacy based on CS2 and CS3 data

Descriptive summary statistics:

Descriptive summary statistics for absolute values, change or percent change from ISIS 420915 baseline, if applicable, will be provided by analysis visits for below endpoints based on 420915 FAS, unless specify.

- mNIS+7 Composite Score (On-Treatment)
- mNIS+7 Composite Score (On-Treatment) by IM
- Modified +7 and +7 Composite Scores (On-Treatment)
- NIS+7 Composite Scores (On-Treatment)
- NIS Composite and Component Scores (On-Treatment)
- Modified +7 Component Scores (On-Treatment)
- +7 Component Scores (On-Treatment)
- Norfolk QOL-DN Total Score (On-Treatment)
- Norfolk QOL-DN Total Score (On-Treatment) by IM
- Norfolk QOL-DN Symptoms Domain Score (On-Treatment) Stage 1 Patients
- Norfolk QOL-DN Physical Functioning/Large Fiber Neuropathy Domain Score (On-Treatment)
 Stage 2 Patients
- Norfolk QOL-DN Domain Scores (On-Treatment)
- NSC Total Score and Domain Scores (On-Treatment)
- Modified Body Mass Index and Body Mass Index (On-Treatment)
- Transthyretin (TTR) and Retinol Binding Protein 4 (RBP4) (On-Treatment)
- Transthyretin (TTR) (On-Treatment) by IM
- SF-36 Component Summary Scores and Domain Scores (On-Treatment)
- NT-proBNP Result (pmol/L) and Log-Transformed NT-proBNP Result (On-Treatment), outputs will be repeated based on ISIS 420915 CM-ECHO set
- mNIS+7, NIS+7, NIS, Modified +7, +7 Composite and Component Scores (Post-Treatment)
- Norfolk QOL-DN Total and Domain Scores (Post-Treatment)
- SF-36 Scores (Post-Treatment)
- NSC Score (Post-Treatment)
- Global Longitudinal Strain (%) (On-Treatment) based on ISIS 420915 Enrolled Patients, ISIS 420915 ECHO Subgroup, and ISIS 420915 CM-ECHO Set
- Assessment of Global Left Ventricular Size and Function LV Mass (g) (On-Treatment) based on ISIS 420915 Enrolled Patients, ISIS 420915 ECHO Subgroup, and ISIS 420915 CM-ECHO Set
- mNIS+7 Composite Score: Response Rate by Threshold Value by Visit (On-Treatment) based on ISIS 420915 FAS

- Summary of PND Score Shift from Baseline by Visit (On-Treatment) based on ISIS 420915
 FAS
- Summary of PND Score Change from Baseline by Visit (On-Treatment) based on ISIS 420915
 FAS
- Summary of Select Questions from NSC (On-Treatment) and (Post-Treament) based on ISIS 420915 FAS

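### The OLE mNIS+7 responder analysis counts early terminators as non-responders, but its FAS denominator omits dosed patients who leave before any OLE efficacy score

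*Combined protocol and SAP*

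**What the plan says.** SAP 3.4.2.1 sets up the responder analysis to examine "whether improvement in response is consistent over a range of response thresholds using the OLE study FAS". A responder at a visit is a patient whose mNIS+7 change from the parent study baseline is at or below a threshold; nine thresholds from 0 to 30 points are listed. On failures it says: "Evaluable patients that terminate treatment early irrespective of the reason or had missing the respective post-baseline visit" data are non-responders. Section 3.4.2.2 repeats this from the OLE study baseline.

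SAP 3.2.2 limits the OLE FAS to enrolled patients with at least one OLE injection "who have at least one post-baseline efficacy assessment for the mNIS+7 score or" the Norfolk QOL-DN total score, collected after CS3 Study Day 1.

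Each visit is further restricted to evaluable patients, "defined as patients who are in the study longer than the upper bound of analysis visit window for that visit". The worked example for Week 26 then uses a different quantity: "data cut date – first dose date) was more than 206 days".

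SAP 9.1 does not list the responder analysis among those dropped from the final analysis. SAP 9.2.2.3 keeps a combined-study version, "mNIS+7 Composite Score: Response Rate by Threshold Value by Visit (On-Treatment"), on the ISIS 420915 FAS.

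**The concern.** Counting early terminators as failures stops a response rate from improving merely because patients who did badly have left. A denominator that requires a post-dose efficacy score partly undoes this. The patients it removes would all have been non-responders, and they are absent at every visit and every threshold.

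The rates are shown for both parent-study groups. Former placebo patients first receive the drug in the OLE, whereas former active patients were generally admitted without significant tolerability problems (protocol 5.1). Early loss could therefore differ between the two curves. That is inference: the documents report no dropout figures.

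The second matter is drafting. The sentence defining evaluable patients and the example beside it give different rules, and a programmer could follow either.

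**Working it through.** **1. The plan's own figure.** SAP Appendix 3, Table 1 puts the Week 26 mNIS+7 target at Day 176 with a half-width of 30 days: 176 + 30 = 206, as in the example. The other upper bounds also reproduce: 358 + 30 = 388, 540 + 30 = 570, 722 + 30 = 752, 904 + 30 = 934 and 1086 + 45 = 1131.

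**2. Whom the FAS omits.** The first scheduled OLE mNIS+7 and Norfolk assessments are at Week 26 (protocol 6.1.2 and Appendix A). Take dosed patients with enough time between first dose and data cut:

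| Patient | In OLE FAS? | Treated as |
|---|---|---|
| Has an OLE score, later stops early | Yes | Non-responder |
| Leaves before Week 26, assessed at early termination | Yes | Non-responder |
| Leaves before Week 26, not assessed | No | Not counted |

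The third row can occur. Protocol 8.9 only encourages the early termination visit, and it ends observation at once when consent is withdrawn. A patient who dies before Week 26 cannot attend.

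**3. Size.** Let R be the responders at a visit, N the dosed patients with enough potential follow-up, and f the fraction of N without any OLE score. No unassessed patient can be a responder, so R is the same under both denominators:

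- all dosed: R / N
- FAS: R / [N(1 − f)]
- ratio: 1 / (1 − f)

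The documents give no f. For assumed values: 1/0.97 = 1.031, 1/0.95 = 1.053 and 1/0.90 = 1.111.

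**4. Illustration in points.** Take N = 135, the approximate number eligible (protocol 3.3). Assume that all have enough potential follow-up, 20% terminate early and half of the rest respond. Then 27 leave, 108 remain and 54 respond.

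| Leavers with no OLE score | Rate on FAS |
|---|---|
| 0 | 54/135 = 40.0% |
| 3 | 54/132 = 40.9% |
| 7 | 54/128 = 42.2% |
| 14 | 54/121 = 44.6% |

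The all-dosed rate is 40.0% throughout, so the excess runs from 0 to 4.6 points. The last row needs about half of the leavers to be unassessed (f = 14/135 = 10.4%).

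**5. The evaluability wording.** The defining sentence depends on how long the patient was in the study. The example depends only on how long the patient could have been followed. Read literally, the sentence could even drop a Week 156 completer. With the visit 10 days late and two weeks allowed for the second mNIS+7, the last assessment falls by Day 1086 + 10 + 14 = 1110, before Day 1131. Post-treatment follow-up may be omitted for a patient who continues the drug by another route (protocol 6.1.3).

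The example needs a data cut date. SAP 3.2.1.4 mentions one only for interim analyses. The final analysis follows study completion and database lock (SAP 3.2.1 and 5), with no cut date named.

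**The case against.** The FAS is the protocol's own efficacy population (10.3 and 10.6), and the non-responder rule can be read as operating inside it. The early termination visit schedules two mNIS+7 assessments in Years 1 to 3 and a Norfolk questionnaire, and one score on either instrument is enough for the FAS. SAP 3.2.3 tabulates the FAS and Safety Set by parent-study group, so the number excluded will be visible. Evaluable patients with a missing visit also count as non-responders, including visits missed because of COVID-19, and that lowers the rates. There are no formal hypotheses (SAP 1.3).

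Much of this stands. The loss may be small, it can be counted from planned tables, and no inference depends on it. But the early termination visit is not assured, and a tabulated count does not correct the rate. The missing-visit rule applies to assessed patients under either denominator, so it does not offset the exclusion.

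A reader might infer more from the phrase about being in the study: that it removes most or all early terminators. On that reading, 50% response among those remaining would be reported as 50% with 10% to 30% dropout, when the intended rate is 0.5 × 0.9 = 45% down to 0.5 × 0.7 = 35%. The documents do not support this. The example counts from first dose to data cut, and the non-responder rule presupposes that early terminators can be evaluable. Stopping treatment is also not leaving the study: protocol 8.8 encourages such patients to stay. A patient who stops at Day 150 and completes 13 weeks of follow-up reaches Day 150 + 91 = 241, beyond Day 206.

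A reader might also carry the OLE exclusion over to SAP 9.2.2.3. The ISIS 420915 FAS (9.2.2.1) draws on the CS2 or CS3 FAS, so a patient treated with the drug in the parent study and in its FAS stays in without an OLE score.

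**Conclusion.** The concern holds for the denominator in SAP 3.4.2.1 and 3.4.2.2. Dosed patients who leave before any OLE mNIS+7 or Norfolk score are omitted when they should count as non-responders, and the error has one direction. Its size is 1/(1 − f), a relative rise of about 3% to 11% for f between 3% and 10%. That range is an assumption. The effect is zero if every early leaver has an early termination assessment.

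The evaluability wording is a separate, smaller fault. The example shows that potential follow-up is intended, but the defining sentence contradicts it and the final analysis lacks the date the example needs. The output is descriptive, so only the reported rates are at stake.

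**What to change.** In SAP 3.4.2.1 and 3.4.2.2:

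- Use all enrolled patients with at least one OLE dose (the Safety Set patients) as the responder denominator. Group them by randomised parent-study arm, as SAP 3.2.1 requires for efficacy.
- Define evaluable as the data cut-off date (database-lock date for the final analysis) minus CS3 Study Day 1 exceeding the window's upper bound, regardless of when the patient left.
- Delete the wording about being in the study longer than the bound.

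In SAP 9.2.2.3, do not use an OLE-dosed denominator: it would drop patients treated in CS2 who never entered the OLE. Use all patients with at least one ISIS 420915 dose in CS2 or CS3, and state the evaluability rule there with potential follow-up counted from Day 1 of ISIS 420915.

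The cost is SAP wording and a change of denominator, with no new data. Response rates may come out slightly less favourable.
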